D.1.1 Overview and Design. The proposed pilot study is designed as a culture-directed versus empiric antibiotic strategy for patient-reported UTI symptoms in older women. (Figure 2) Over 12 months, we will recruit 70 women with rUTI. Following enrollment, patients will be randomized in a 1:1 ratio to one of two groups. Patients assigned to the culture-directed arm will await results of urine culture prior to potentially receiving antibiotics and those assigned to the empiric arm will be prescribed immediate antibiotics from an established list of commonly prescribed antibiotics. Participants will be sent electronic questionnaires after urine culture results and then weekly for a total of 4 weeks. The primary outcome is feasibility of trial defined as recruitment of 10% of eligible participants with 70% adherence to study protocol.

D.1.2 Recruitment and Subject Eligibility. Women age ≥65 years⁶¹ with diagnosis of recurrent UTI (rUTI) will be recruited from: 1) UPMC WCBPH faculty practices or 2) CTSI Pitt+Me® Research Registry. Eligibility criteria are listed in Table 2.

Rationale for Inclusion Criteria: We will include participants with patient reported recurrent UTI to allow for a pragmatic study design and generalizability. Additionally, our definition of patient reported UTI is like other RCTs evaluating non-antibiotic options as compared to antibiotic strategies for UTI treatment.^{43,62} We will exclude participants with features of complicated UTI in the setting of structural or functional abnormalities or instrumentation /catheterization^{4,63} Eligibility is limited to female biologic sex given the differential risk profile of males and females who experience recurrent UTIs.

D.1.3 Study procedures (Figure 2).

D.1.3.1 – Screening and Enrollment Procedures.

Information on the REDUCTION trial will be broadly disseminated in the University of Pittsburgh faculty practices at the WCBPH, through IRB approved brochures, social media ads, institutional (MWRI) and CTSI websites. Interested women will be encouraged to contact the research staff for more information. Women who meet eligibility criteria after screening will be provided a consent form via their preferred method (electronic or paper).

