
Pelvic floor distress inventory, PFDI-20; Urinary Tract Infection Symptom Assessment, UTISA
 * Adverse events will include either antibiotic related side effects, signs/symptoms of pyelonephritis and/or urosepsis or other serious adverse events

D.1.7. Data analysis.

Specific aim 1A) To evaluate the feasibility of recruiting eligible participants into a randomized trial of a culture-directed versus empiric antibiotic strategy for patient-reported UTI symptoms in older women.
 All outcomes for the feasibility assessment will be descriptive using numbers and proportions of patients and 95% CIs. We will report the number of patients assessed for eligibility along with the numbers excluded based on not meeting inclusion criteria, participation declined, and other reasons.⁷⁴ We will document number and proportion of enrolled participants who were randomized along with the number/proportion who received their

allocated assignment. We will document those lost-to follow-up including potential reasons. These data will provide information on the feasibility of recruiting patients into a future, large randomized, placebo controlled clinical trial. We believe that successfully recruiting 10% of eligible patients (e.g., 6-7 patients per month) will confirm the capacity to recruit for a future trial.

Power calculation:^{75,76} The primary outcome is feasibility which we will define as the ability to recruit 10% of eligible patients. As this is a pilot study, the sample size of 70 patients was determined based on clinical and logistical resources rather than statistical requirements for hypothesis testing. We anticipate screening approximately 1200 potentially eligible patients (based on known clinical data from our practice and current enrollment of women with recurrent UTI in Pitt+Me®) during the 12 months of recruitment (~100 per month) of which at least 800 will be deemed eligible and have UTI symptoms. (~67 per month) This is based on data from our group on urine cultures sent annually and time between UTI episodes.³⁵ A 95% confidence interval (CI) for the recruitment rate provides a 2.4% margin of error (MoE) assuming the true rate is 10%.

Specific aim 1B) To evaluate participant adherence to study procedures.

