Analysis. All outcomes will be described using numbers and proportions of patients or means with confidence intervals. Proportions between groups will be compared with either chi-square or Fischer's exact testing and means will be compared with student's t-testing. Exploratory logistic regression modeling will be utilized to investigate the odds of both initial treatment failure and/or recurrent of UTI symptoms between groups and based on baseline characteristics

Power analysis:^{76,79} As above, we propose a future trial with a primary outcome to be symptom resolution at day 14 defined as 2 or less points (slight, very slight, or no problems) on all five components of the UTI symptom assessment (UTISA).^{43,78} The literature suggests 58-80% of women receiving empiric antibiotics for patient reported UTI will achieve clinical cure by day 3-7 after treatment initiation.^{43,78} Given that only women

with a positive urine culture will be given culture-directed antibiotics, and women in the empiric arm may have to have their antibiotics changed or stopped at the time of culture result, we anticipate a higher proportion of those in the culture-directed arm to have symptom resolution at day 7. Assuming 70% symptom resolution in the empiric arm, a future trial of 262 participants, with 131 per arm, would have 80% power to detect a 15-percentage point difference between groups with a 2-sided alpha of 0.05, while a sample size of 300 would be required assuming 65% resolution. Therefore, we believe that successfully recruiting a total of 70 participants at a rate of 6-7 participants/month will confirm the feasibility of future trial completion in <4 years (equivalent to other trials of antibiotic regimens for symptomatic UTI).^{17,78}

Statistical methods

Primary Outcomes	Statistical analysis
Feasibility: 
 - Number of subjects that were screened for participation - Number and proportion of subjects screened who met inclusion/exclusion criteria - Number and proportion of subjects who either declined participation or were ineligible (including reasons for ineligibility) - Number and proportion of eligible subjects that were enrolled in the study - Number and proportion of subjects enrolled who completed the study - Monthly enrollment rate 	Descriptive analysis = counts and proportions or means with standard deviation

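### The recruitment success rule is inconsistent on the plan's own figures: 10% of eligible women, 70 women in 12 months, and 6-7 per month are three different targets

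*Combined protocol and SAP*

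**What the plan says.** D.1.1 (Overview and Design): "The primary outcome is feasibility of trial defined as recruitment of 10% of eligible participants with 70% adherence to study protocol". The same section sets the size and period: "Over 12 months, we will recruit 70 women with rUTI".

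D.1.7, Specific aim 1A, repeats the percentage in its Power calculation paragraph: "The primary outcome is feasibility which we will define as the ability to recruit 10% of eligible patients". Just before that paragraph it says that "successfully recruiting 10% of eligible patients (e.g., 6-7 patients per month) will confirm the capacity to recruit for a future trial". The monthly figure is therefore an illustration, not a condition. The paragraph also forecasts about 1200 women screened over 12 months, of whom at least 800 (about 67 per month) will be eligible and symptomatic, and gives a 2.4% margin of error for the recruitment rate at a true rate of 10%.

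The Power analysis paragraph under the secondary exploratory aims sizes the future trial at 262, or 300 under a lower resolution rate, and concludes that "successfully recruiting a total of 70 participants at a rate of 6-7 participants/month will confirm the feasibility of future trial completion in <4 years". No percentage appears there.

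The Statistical methods table lists both the enrolled proportion of eligible women and the monthly enrollment rate as feasibility outcomes. Both are descriptive and neither has a threshold.

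**The concern.** Two rules are each said to confirm that a future trial can be recruited, and they measure different things. The share of eligible women who enroll measures how acceptable the trial is. The number enrolled per month determines how long 262 or 300 women will take. One converts into the other only through the monthly flow of eligible women, which is forecast rather than fixed and which the pilot itself will reveal.

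The recruitment criterion is part of the primary outcome of a pilot whose purpose is to inform a definitive trial. If the rules can disagree, and nothing says which governs, the same data can be read as success or failure after they are seen. The disagreement does not need an unusual scenario: it already appears when the plan's stated targets are set against each other.

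**Working it through.** **Inputs.** From D.1.1: 70 women, 12 months, 10% of eligible. From D.1.7, aim 1A: at least 800 eligible in 12 months, 6-7 per month as an example, 2.4% margin of error. From the Power analysis paragraph: future trial of 262 (70% vs 85%) or 300 (65% vs 80%), 80% power, two-sided alpha 0.05, completion in under four years (48 months).

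**1. The plan's own figures.**
- Future trial size: exact power of Fisher's test is 80.1% at 131 per arm and 80.3% at 150 per arm, so 262 and 300 both reproduce.
- Link between the rules: 800/12 = 66.7 eligible per month, and 10% of that is 6.67 per month. This is evidently where 6-7 comes from.
- Margin of error: 1.96 × √(0.10 × 0.90/800) = 2.1%, not 2.4%. Solving for 2.4% gives n = 1.96² × 0.09/0.024² ≈ 600 eligible, or 50 per month.

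**2. Where the rules coincide.** 6/0.10 = 60 and 7/0.10 = 70 eligible women per month.

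**3. The targets against each other.**
- 70/800 = 8.75%, below 10%; 10% of 800 is 80 women, more than the sample size.
- 70/12 = 5.83 per month, below 6-7.

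**4. Accrual time = N / monthly rate.**

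| Rate per month | Months for 262 | Months for 300 |
|---|---|---|
| 5.83 (70 in 12 months) | 44.9 | 51.4 |
| 6 | 43.7 | 50.0 |
| 6.67 (10% of 800 in 12 months) | 39.3 | 45.0 |
| 7 | 37.4 | 42.9 |

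The lower end of the plan's own 6-7 range exceeds 48 months for 300.

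**5. Rate needed for under 48 months.** 262/48 = 5.46 and 300/48 = 6.25 per month; the rate must exceed these. At exactly 10% recruitment that means more than 54.6 or 62.5 eligible women per month.

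**6. A lower flow (assumption: 50 eligible per month).** 10% gives 5 per month and 60 women in a year. The percentage criterion is met, yet 262/5 = 52.4 months and 300/5 = 60 months.

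**7. Precision of the observed rate.** The exact Poisson 95% CI for 70 women is 54.6 to 88.4; divided by 12 months, about 4.5 to 7.4 per month.

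**The case against.** The strongest reply is that the plan does link the two rules. If at least 800 eligible women appear and 10% of them enroll, the rate is at least 6.67 per month and both future sizes accrue in under 48 months. The targets can also be made to agree: at 66.7 eligible per month, 10% recruitment reaches 70 women after 700 eligible, at 700/66.7 = 10.5 months. That stands as arithmetic. But the plan does not say that screening stops at 70, D.1.1 spreads the 70 over 12 months, and the flow of eligible women is an expectation outside the criterion.

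A reader might infer that the plan derives completion in under four years from the 10% rule, so that a slow pilot could pass and make that statement false. The documents do not support this. The duration claim is attached only to 70 women at 6-7 per month, and a slow pilot would fail that condition. What the 10% rule is said to confirm is capacity to recruit, and that is the claim a percentage cannot carry alone. D.1.1 also requires 70% adherence, so 10% recruitment is not the whole primary outcome.

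A reader might also reach for extreme flows, such as half the forecast or 100 eligible per month. The documents give no reason to expect the first, and the second would require every woman in the forecast of about 100 screened per month to be eligible and symptomatic. The point does not need either.

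Nor would a shortfall be hidden: fewer than 70 women would be visible, and the monthly rate is reported. What is missing is a rule for interpreting it.

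**Conclusion.** The point holds as an inconsistency in the recruitment decision rule. On the plan's own figures, full enrollment of 70 from 800 eligible misses the 10% criterion (8.75%), and 70 in 12 months (5.83 per month) misses 6-7 per month. At 5.83 per month, 262 women accrue within four years (45 months), but 300 do not (51 months). Away from the forecast flow, 10% can be met at a rate too slow for either size, as at 50 eligible per month.

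The accrual times assume that the future trial recruits at the pilot's rate. The Power analysis paragraph makes that inference itself, but the documents give no number of sites for the future trial. They cover accrual only, with no allowance for dropout or follow-up. The flow of 50 per month is an assumption. It equals the denominator implied by the 2.4% margin of error, but the plan does not state that denominator, so this is not evidence that the sponsor expects 600 eligible women.

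Data collection is unaffected. What is at stake is whether the pilot's result can be read in only one way.

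**What to change.** Amend D.1.1, D.1.7 (Specific aim 1A) and the Power analysis paragraph together:

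1. Keep 10% of eligible women as the acceptability criterion, and state that it does not by itself confirm capacity to recruit.
2. Base the accrual conclusion on the observed monthly enrollment rate, reported with its 95% CI, against one threshold chosen in advance. Use more than 6.25 per month if the under-four-years claim is to cover both 262 and 300, or at least 5.5 per month with the claim limited to 262 (262/5.5 = 47.6 months). Say whether the point estimate or a confidence limit is compared with it.
3. Reconcile 70 women, 10%, 800 eligible and 6-7 per month. For example, state that 70 is 10% of about 700 eligible and that screening stops when 70 are enrolled, or restate the percentage as 8.75%. State the denominator behind the 2.4% margin of error.
4. Say how a split result is reported, for example as acceptable but with insufficient accrual, or the reverse.

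The cost is wording; both quantities are already collected. There are two real downsides. A pilot exactly on plan, at 5.83 per month, would not support the under-four-years claim for 300. And the interval, about 4.5 to 7.4 per month, covers both thresholds, so the pilot will inform the accrual question without settling it.

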- This visit will first take place with a research coordinator where the participant will be allowed to ask any final questions about their consent which will then be signed either on paper or electronically.
- Final eligibility will be determined by a licensed medical provider on the research team by ensuring the participant is not experiencing any symptoms of pyelonephritis and/or sepsis.
- Consented study participants will then complete baseline questionnaires including the Urinary Tract Infection Symptom Assessment (UTISA)⁶⁸ and the pelvic floor distress inventory short form (PFDI-20).⁶⁹
- Participants will submit a urine specimen for urine culture and urinalysis either in-person at one of our Women's Center for Bladder and Pelvic Health faculty practices or a local laboratory

Randomization: Participants will be randomized by the study team to either the “Culture-directed Antibiotic Treatment” or “Empiric (Immediate) Antibiotic Treatment” Group in a 1:1 allocation scheme, with randomization using permuted blocks of 4 or 6.

D.1.3.3 Antibiotic Treatment Strategy. All participants will be allowed to use acetaminophen, non-steriodals, and/or phenazopyridine.

Culture-directed Antibiotic Treatment: Participants will be directed to refrain from taking antibiotics until results of urine culture are reported, which is expected within 48-72h.

Empiric Antibiotic Treatment Participants will be prescribed empiric antibiotics in accordance with our stepwise protocol below.

Antibiotic Protocol. For participants in the empiric Rx arm, we will choose an antibiotic with consideration of patient reported allergies, current medications and current IDSA guidelines.⁷⁰ If there is a contraindication to the first antibiotic on the list they will progress to the next option until a suitable selection is achieved.

Antibiotic Protocol:

1. Nitrofurantoin 100 mg PO BID x 5 days
2. Trimethoprim/Sulfamethoxazole 875/125 mg PO BID x 5 days
3. Fosfomycin 3 g once
4. Cephalexin 500 QID x 5 days
5. Ciprofloxacin 500 mg PO BID x 5 days

D.1.3.4 Antibiotic management after urine culture results. All participants will be called with the results of their culture. Participants who register for *MyUPMC*, a no-cost, proprietary secure email service, will also receive the urine culture result by email. Cultures with result of “mixed flora” will be considered contaminated and be managed as negative.⁷¹

Culture-directed Antibiotic Treatment.

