- Those with a negative urine culture will not be prescribed antibiotics and will be followed per protocol.
- Those with a positive urine culture who *report persistent UTI symptoms* will be given antibiotics following the priority list above with consideration to reported antimicrobial sensitivities.
- Those with a positive urine culture who *report resolution of UTI symptoms* will not be given antibiotic

Empiric Antibiotic Treatment.

- Those with a negative urine culture will be told to stop antibiotics
- Those with a positive urine culture sensitive to the empiric antibiotic will be instructed to complete the full course of their antibiotics
- Those with a positive culture resistant to empiric antibiotic will be given an alternative antibiotic per antibiotic protocol and will be followed per protocol. If there are no oral antibiotic options with patient-specific and antimicrobial sensitivities, we will engage local infectious disease physicians for management as per standard clinical protocols.

[figure not shown]
D.1.6. Study follow-up assessments.

All participants will be followed with electronic surveys via Research Electronic Data Capture (REDCap) software, which is a browser-based, metadata-directed EDC software and workflow methodology for designing

clinical and translational research databases,⁷² on day 2-3 (after result of urine culture). To avoid limiting enrollment to only those with access to technology, our research coordinator can also call and administer the questionnaire by phone to ensure ability to access and complete electronic materials. Follow-up assessments will be completed weekly for a total of 4 weeks. These will include UTISA questionnaire,⁶⁸ antibiotic associated side effects, use of other symptom mitigating remedies, and adherence to assigned study arm.

Participants will be provided with a clinical line to call 24/7 with report of worsening symptoms which will be discussed with the PI, [name] for determination of antibiotic prescription and if participants report fevers or chills this will prompt an in-person evaluation in clinic during business hours or the emergency department after hours. If participants call to report new symptoms during the study course, a repeat urine culture will be obtained.⁷³ Given that these episodes could be considered either a recurrent or incompletely treated infection we plan to manage these per clinical care and not based on the participants initial study arm.

Figure 2: Study Flow Diagram

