For a larger trial, electronic surveys may significantly reduce research coordinator burden. To evaluate feasibility of this approach we will administer electronic surveys through Research Electronic Data Capture (REDCap) software.⁷² Surveys are sent via email and can be accessed through either a laptop, desktop or smart phone. Participants will also be called at day 2-3 (after urine culture results) and then weekly to assess issues with electronic materials. We will evaluate proportion of those with electronic success and investigate demographic variables that may be associated with inability to utilize electronic materials. To assess patient adherence to study procedures, defined as completion of all follow-up questionnaires, we will describe the percentage of enrollees who completed 100% of study procedures, 80% to 100% of study procedures and 50% to 80% of study procedure. A priori, we believe that compliance with 70% of study procedures will demonstrate satisfactory patient adherence to protocol. If the underlying adherence rate is 70%, a sample size of 70 provides a 10.1% MoE.

Exploratory Aim: To explore the safety of a culture-directed UTI treatment strategy and preliminary secondary outcomes of assigned treatments.

Safety Aims⁶²

1. Adverse events per group (most likely antibiotic side effects (i.e., gastrointestinal distress, antibiotic related diarrhea, rash) between groups.
2. Serious adverse events per group (defined in line with FDA reporting guidelines as a medical event that does one or more of the following: results in death, is life - threatening, requires inpatient hospitalization or prolongation of existing hospitalization, results in persistent or significant disability/incapacity, or is a congenital anomaly/birth defect.⁷⁷

Analysis. We anticipate that adverse events will be reported relatively infrequent.⁷⁸ All outcomes will be described using numbers and proportions of patients. Proportions between groups will be compared with either chi-square or Fischer's exact testing.

Secondary exploratory aims.

Proportion of those with clinical cure (as 2 or less points (slight, very slight, or no problems) on all five components of the UTISA (ref) at day 14 (***future trial primary outcome***)

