Adherence: 
 - Number of those that completed all study procedures - Number of subjects that took alternative agents taken by subjects for management of symptoms - Number of subjects in the culture-directed arm that acquired off-protocol antibiotics for their symptoms - Number of subjects able to complete electronic surveys 	Descriptive analysis = counts and proportions
Secondary Outcome	
Proposed primary outcome for future trial (Clinical Success at 14 days UTISA 1-3,5<=1)	Descriptive analysis = counts and proportions Comparative = Chi-square

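### Staff calls coincide with every electronic survey, and the planned outputs do not separate unprompted from call-prompted completion, so they do not show what electronic follow-up achieves with less staff contact

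*Combined protocol and SAP*

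**What the plan says.** Section D.1.7, Specific aim 1B, opens with the motive: "For a larger trial, electronic surveys may significantly reduce research coordinator burden". It then states the test: "To evaluate feasibility of this approach we will administer electronic surveys through Research Electronic Data Capture (REDCap) software". The contact schedule follows in the same paragraph: "Participants will also be called at day 2-3 (after urine culture results) and then weekly to assess issues with electronic materials".

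The survey schedule in section D.1.1 has the same time points: "Participants will be sent electronic questionnaires after urine culture results and then weekly for a total of 4 weeks". Section D.1.6 repeats that schedule and, so that women without access to technology are not shut out, adds that "our research coordinator can also call and administer the questionnaire by phone". Section D.1.3.4 has a clinical contact near the first survey: "All participants will be called with the results of their culture".

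Three outputs bear on the question:

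- a proportion with electronic success, which aim 1B does not define;
- a row in the Statistical methods table, under Adherence: "Number of subjects able to complete electronic surveys";
- adherence, defined in aim 1B as finishing every follow-up questionnaire, with a 70% benchmark and no restriction on mode.

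The calls are not limited to women who have not responded. The plan names no field for the mode of completion, the time of the call or coordinator time.

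**The concern.** The motive for electronic surveys is to spend less coordinator time. In the pilot, every participant has a staff contact scheduled at each survey point. A call about problems with the survey may plausibly lead someone to complete it. If so, completion in the pilot reflects electronic delivery plus the call, and the planned summaries do not show how much belongs to each.

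This matters for designing the larger trial. Its proposed primary outcome is symptom resolution on the UTISA at day 14, which these surveys collect. If the calls were reduced on the strength of the pilot and completion then fell, that outcome would lose data. If the calls were kept, the hoped-for saving would not arrive.

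**Working it through.** **The plan's own figure.** Aim 1B gives a margin of error of 10.1% for 70% adherence with n = 70. The usual 95% half-width is 1.96 × √(0.70 × 0.30 / 70) = 0.107, or 10.7%, so the stated figure is not reproduced. That is a separate, minor matter, and nothing below depends on it.

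**The time points side by side.**

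| Time point | Survey (D.1.1, D.1.6) | Staff contact |
|---|---|---|
| Day 2-3, after culture | Yes | Aim 1B call; also the culture-result call (D.1.3.4) |
| Weekly to 4 weeks | Yes | Aim 1B call |
| Any | Phone administration possible (D.1.6) | Coordinator |

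No survey point is free of a scheduled call.

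**Why the observed rate does not give the unaided rate.** Let u be the share completing unaided and c the share of the remainder who complete because of a call. The observed rate is u + (1 − u)c. The values of u and c below are assumed; the documents give neither.

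- u = 0.70, c = 0: 0.70
- u = 0.60, c = 0.25: 0.60 + 0.40 × 0.25 = 0.70
- u = 0.40, c = 0.50: 0.40 + 0.60 × 0.50 = 0.70

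The planned outputs would look the same in all three cases.

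**Illustration on all-survey completion.** Assumptions: five surveys (day 2-3 plus four weekly), independent of each other, 85% unprompted completion per survey, and the 70% rule read as 70% of participants completing all surveys.

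- Per-survey rate needed: 0.70^(1/5) = 0.931
- No calls: 0.85^5 = 0.444
- Calls recover half of the missed surveys: (0.85 + 0.15 × 0.50)^5 = 0.925^5 = 0.677
- Calls recover three quarters: (0.85 + 0.15 × 0.75)^5 = 0.9625^5 = 0.826

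On this reading, only the three-quarters case crosses 70%.

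**The other reading of the rule.** Aim 1B can also be read as each participant completing at least 70% of procedures, that is, at least 4 of 5 surveys. At 85% per survey with no calls, 0.85^5 + 5 × 0.15 × 0.85^4 = 0.444 + 0.392 = 0.835. The benchmark is then met without any calls.

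**Scale of the contact.** At four or five calls per participant (assumed), the proposed trial of 262 to 300 participants needs between 4 × 262 = 1,048 and 5 × 300 = 1,500 calls.

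**The case against.** Much of the case on the other side stands.

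- *The aim is adherence.* Aim 1B evaluates adherence to study procedures, and these procedures include the calls. As an estimate of adherence under this protocol, the result is not biased by them. This stands. The point concerns only the further inference about staff burden, which the same paragraph invites.
- *The plan speaks of reducing burden.* A reader might infer that the pilot must show electronic surveys working with no coordinator effort, or that the larger trial will drop the calls. The documents say neither.
- *The electronic measure concerns ability.* On its natural reading, a phone-administered survey is not an electronic completion. This stands. What that measure leaves unseparated is prompted and unprompted electronic submission; phone completion is mixed in only within adherence.
- *The calls and phone administration are separate provisions.* A reader might infer that staff complete the survey during the weekly call. The stated purpose of phone administration is access ("our research coordinator can also call and administer the questionnaire by phone to ensure ability to access and complete electronic materials"), and nothing places it on the scheduled call. Nor does the plan describe the calls as reminders; prompting is plausible, not stated.
- *The pass-or-fail illustration is fragile.* It needs assumed rates and one reading of the 70% rule. Positive correlation between one woman's surveys would raise all-five completion above 44%. It shows a mechanism and is not a forecast.
- *Time-stamps could recover part of the answer.* They could, given call times, but the plan specifies neither the fields nor the analysis.

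**Conclusion.** The point holds in limited form. As planned, the pilot can describe who is able to use the surveys, what problems arise, and adherence with calls in place. Its outputs do not show what electronic follow-up achieves with less staff contact, because submissions before and after a call are pooled and adherence accepts any mode.

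The size is unknown. On assumed values, an observed 70% is compatible with unaided completion anywhere from 40% to 70%, and a wider range of assumptions would widen that span.

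Two stronger conclusions should not be drawn. One is that the pilot is incapable of informing the question: with mode and call times recorded, it can do so in part. The other is that the calls decide whether the 70% benchmark is met: that depends on assumed rates and on reading the benchmark as 70% of participants completing all surveys. The electronic-success measure itself has no threshold, so no go/no-go decision rests on it directly.

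**What to change.** Leave the timing of the calls, the culture-result call and the phone option as they are. Moving the calls to after each survey window is a debatable trade-off: help could come too late for the survey that supplies day-14 UTISA.

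1. For each survey, record the mode of completion and the date and time of that time point's call.
2. Define the main electronic-success measure as an electronic submission made by the participant and time-stamped before that time point's staff call.
3. At each time point, report three counts: electronic before the call, electronic after the call, and by phone.
4. Report all-survey completion overall and restricted to pre-call electronic submissions.
5. State that earlier calls may influence later surveys, so the pre-call rate leans upward as an estimate of unaided completion. A call made soon after the survey is sent pulls the other way by leaving little time to respond unaided, and the call times will show where this happened.
6. State whether the day 2-3 call and the culture-result call are one contact, since that affects how the first time point is read.
7. Label any numerical illustration as assumed, and say that it reads the 70% rule as 70% of participants completing all surveys.

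The cost is a few lines of analysis text and two data fields, about 70 × 5 = 350 survey records if there are five surveys each. The reported electronic rate may be lower than under the present wording.
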